4.0 Ethical Considerations

Eligible participants may only be included in the study after providing written consent to participate. Before the study session, each participant will be provided with details of the structure, confidentiality requirements and anonymity of the research, and will be invited to give informed consent via signing of an informed consent form (Appendix B).

At enrolment each participant will be assigned a unique participant number that will be used for data collection, and subsequent analysis and reporting purposes. All non-identified data will only be accessible by members of the research group for the specific purpose of the study.

4.1 Consent forms

All patients will consent to participation in this IRB approved, prospective observational study per the consent form in appendix B.

4.2 Compensation

Patients will not be compensated for this study as incentivizing them might potentially affect the outcome of the study.

5.0 Study Outline

Timescale	Tasks & Environment		
	Surgeon Clinic	PT Clinic	Home
2-3 weeks prior to surgery	
 ○ Patient Consent ○ Onboarding with MotionSense (incl. timing) ○ Fill out patient journal ○ Assign pre-operative exercises 	N/A	N/A
Prior to surgery	N/A	N/A	
 ○ Home exercises ○ Gait assessment (2x / week) ○ Pain scores ○ PROMs (KOOS & PROMIS10)
Day of Surgery	N/A	N/A	N/A
Discharge	
 ○ Re-install MotionSense sensors ○ Complete LACE questionnaire ○ Assign early-post-operative exercises 	N/A	N/A
After discharge	
 ○ Log complications / interactions with the clinic (e.g. additional patches) 	Log assigned exercises and reason for assignment Log active / passive range of motion	
 ○ Perform home exercises using sensor ○ Wear sensors during daily activities ○ Complete gait assessments (2x / week) ○ Report pain scores ○ Complete PROMs ○ Upload wound pictures as deemed necessary
90d after surgery	
 ○ Phone interview with patient 	N/A	N/A

## 1.1 Study Objectives

### 1.1.1 Objective Analysis

The primary objectives of this study are to evaluate:

- **OBJ1.1:** Evaluate patient and practice compliance with the MotionSense wearable system
  - Hours of MotionSense use per day in office
  - Number of days use after / prior to surgery
  - Filled out questionnaires
  - Home exercise program
  - Patient onboarding time in surgeon clinic
- **OBJ1.2:** Document home exercise program prescribed to patients throughout their individualized recovery progress by surgeons and physiotherapists

The secondary objectives of this study are:

- **OBJ2.1:** Correlate functional and patient reported outcome metrics
- **OBJ2.2:** Evaluate convenience of using the MotionSense system
  - Number of leg registrations performed (per day)
  - Number of (weekly / daily) patches used
  - Number of wound pictures shared with surgeon office
- **OBJ2.3:** Establish normative recovery data for the primary outcome metrics captured by the MotionSense system
  - Daily VAS pain scores
  - Daily Steps
  - Knee active and weight bearing time
  - Range of Motion
  - Gait quality

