3.0 Research Plan

3.1 Study Design

The study is designed as a prospective, observational study including a maximum of 50 patients that are scheduled for total knee arthroplasty and will be participating in outpatient physiotherapy as part of their standard of care recovery pathway.

The study aims to replicate an actual use scenario of the Motionsense system, involving longitudinal follow-up of the patients starting 2-4 weeks prior to surgery up to 90 days after surgery. Patients will be recruited through the surgeon clinic, and subsequently use the MotionSense system at home and in collaboration with their physiotherapist who will assign adequate exercises to the patient. At the end of their 90-day recovery window, the patients' experience with the MotionSense system will be evaluated using a phone interview by the research nurse.

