3.7 Participants

The study participant will represent a range of typical intended users of the Motionsense System. More specifically, the following selection criteria will be used:

- Planned to undergo unilateral total knee surgery in the coming 4 weeks
- Age 50 to 80
- BMI not exceeding 35
- Owns a smartphone (agnostic to brand or type)
- Patient does not have severe skin conditions that would potentially result in irritation or harming the skin when applying the weekly patches.

Beyond that, the study should aim to recruit patients with various socio-economic backgrounds, various levels of motivation as well as a wide range of educational level.

A total of 50 participants will be recruited for the study. Recruitment for this study will be managed by the Principal Investigator. Through the orthopaedic practice, the surgeon office has regular access to patients matching the profile of intended users. In addition, the surgeon has close contact with the participating physiotherapists while the research nurse is employed by the surgeon office. Participants will provide their written informed consent prior to participation (Appendix F).

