## 1.3 Missing Data

No missing data will be imputed.

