## 1.4 Statistical Methodology

### 1.4.1 Data Summary

Descriptive statistics were computed for demographics parameters and study measures. For continuous data, the N, mean, median, standard deviation, interquartile range, minimum and maximum were computed. For categorical data, the frequency was computed. Correlation was calculated using Spearman's rank correlation coefficient.

Documentation of statistical analyses with Python v3.9.0 will be maintained.

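### The pre-operative day count in OBJ1.1 has no days-available denominator, so it mixes surgical lead time with compliance

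*SAP*

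**What the plan says.** OBJ1.1, the first primary objective, is about compliance by patients and by the practice. One of its listed measures is "Number of days use after / prior to surgery"; another is "Hours of MotionSense use per day in office". Protocol 2.0 carries the same list. On method, SAP 1.4.1 states: "Descriptive statistics were computed for demographics parameters and study measures". It then names the usual summaries for continuous and categorical data. SAP 1.3 states: "No missing data will be imputed".

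The time a patient has the system before surgery is given in three ways:
- Protocol 3.1 has follow-up "starting 2-4 weeks prior to surgery up to 90 days after surgery".
- Protocol 5.0 places consent and onboarding "2-3 weeks prior to surgery".
- Protocol 3.7 admits patients who are "Planned to undergo unilateral total knee surgery in the coming 4 weeks", which sets an upper limit but no lower one.

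Protocol 3.2 expects daily use, puts discharge on day 2 to 3, and gives a ceiling of 120 days in a row. Protocol 3.8 has wear time recorded as an hourly total. No section gives a denominator for the day count or a minimum wear time that makes a day count as used.

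**The concern.** Compliance is use relative to expected use, and the expected use here is every day. A number of days carries that meaning only if the number of possible days is the same for everyone or is reported with it. Before surgery it is neither: it depends on how far ahead the operation was booked when the patient was onboarded. A patient with a short lead and perfect use can have the same count as a patient with a long lead who left the sensors off half the time.

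No hypothesis test rests on this measure. But description is what this objective delivers, and a reader of the planned table could not recover from a mean or median count how well patients complied before surgery. The undefined day of use adds to this. Without a threshold, a few minutes and a full day of wear may count alike, and the ratio cannot be computed in a reproducible way.

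**Working it through.** **Inputs**
- Lead time: 14 to 28 days (Protocol 3.1); 14 to 21 days (Protocol 5.0); at most 28 days, no minimum (Protocol 3.7).
- End of follow-up: day 90 (Protocol 3.1).
- Start of post-operative use: sensors put back on at discharge (Protocol 5.0), on day 2 to 3 (Protocol 3.2).
- The plan's own duration figure: a ceiling of 120 days (Protocol 3.2).

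Day limits are approximate; counting end days inclusively shifts them by about one.

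**1. The plan's own figure.** Longest lead plus follow-up is 28 + 90 = 118 days, which is 2 days (2/120 = 1.7%) below the ceiling of 120. With the window in Protocol 5.0 the maximum is 21 + 90 = 111. The ceiling thus fits a four-week lead. It is a maximum for the study and does not give each patient's days available.

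**2. Same count, different use.** Use = days used / days available. For a count of 14 days:
- 14-day lead: 14/14 = 100%
- 21-day lead: 14/21 = 67%
- 28-day lead: 14/28 = 50%

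**3. Same use, different count.** With use assumed at 80% for everyone:
- 0.8 × 14 = 11.2 days
- 0.8 × 21 = 16.8 days
- 0.8 × 28 = 22.4 days

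The ratio of longest to shortest is 28/14 = 2 under Protocol 3.1 and 21/14 = 1.5 under Protocol 5.0, whatever level of use is assumed. Under Protocol 3.7 the ratio has no stated limit, because there is no minimum lead.

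**4. Averaging does not remove it.** Assume leads spread evenly over the window. The mean lead is (14 + 28)/2 = 21 days under Protocol 3.1 and (14 + 21)/2 = 17.5 days under Protocol 5.0. A cohort mean count of 14 days then corresponds to 14/21 = 67% or 14/17.5 = 80% of available days. The actual dates would show which applies, but only if the summary uses them.

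**5. After surgery.** Days available are 90 − 2 = 88 or 90 − 3 = 87. The ratio is 88/87 = 1.01, so for a patient followed to day 90 the count already reads almost as a proportion. Total days available run from 14 + 87 = 101 to 28 + 88 = 116 (Protocol 3.1 window), so the post-operative part is 88/116 = 76% to 87/101 = 86% of the whole.

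**The case against.** The strongest case on the other side is that this is a small gap in a descriptive study. Three-quarters or more of the exposure lies after surgery, where the window hardly varies. The phrase is a bullet in a list of objectives, so the documents are silent on derivation and do not choose an undivided count; an analyst may well report a percentage. Protocol 3.2 gives the expected frequency and a maximum duration, and the closing interview asks when use stopped.

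Much of this stands, and it limits the point to the pre-operative count and to a minor rating. It does not remove the point. The SAP is where the derivation should be stated, and the ceiling and the interview do not supply each patient's days before surgery.

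A reader might also infer stronger things that the documents do not support:
- *That lead time accounts for a known share of the variation in the count.* This would need a mean and spread of compliance, which neither document gives, and no planned analysis is shown to use that variation.
- *That the initial patch supply caps the count.* Protocol 3.6 offers refills, Protocol 5.0 has the clinic "Log complications / interactions with the clinic (e.g. additional patches", and patches used are already an OBJ2.2 measure.
- *That mean hours per day will be inflated by dropping days without wear.* As worded, that measure concerns use in the office, while daily use is at home. Until the wording is settled, no size can be put on it.

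**Conclusion.** The point holds for the pre-operative count. As listed, it mixes surgical lead time with compliance: equal counts can stand for 50% or 100% use over the Protocol 3.1 window, and equal use can give a two-fold difference in counts. These two results rest only on the stated window and on daily use being expected. The 67% and 80% cohort figures also assume evenly spread leads.

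It would be wrong to read this as a fault of equal weight in the post-operative count. There the problem is small, and a rule is needed mainly for patients who die or withdraw before day 90. The missing day-of-use definition matters because the ratio cannot be computed without it; alone it is missing detail. The rule for hours on days without wear is conditional on what the office wording means. Severity: minor.

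**What to change.** In the SAP:
1. Report days used / days available beside the raw count, separately for two periods: onboarding to the actual surgery date, and discharge to day 90. End the second at death or study withdrawal, but not at simple non-use; otherwise patients who stop wearing the sensors would appear fully compliant.
2. Define a day of use by a stated minimum of recorded wear time, using the hourly totals in Protocol 3.8.
3. Clarify the office wording of the hours measure. If home use is meant, state that an available day without wear counts as 0 h.

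In the protocol, reconcile the enrolment windows in 3.1, 3.7 and 5.0.

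The cost is SAP wording and a few derived variables. The surgery date is already needed to split use before and after surgery, and wear time is already captured. There are two drawbacks. Days lost to device failure or readmission may count as non-use; Protocol 3.2 has readmissions logged, but neither document describes a log of device failures or says that readmission dates are kept. Also, SAP 1.4.1 is written in the past tense, so analysis may already have begun; a wear threshold set after data have been seen should be labelled post hoc.

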## 1.2 Safety

### 1.2.1 Safety Parameters

Safety parameters include all adverse events.

## 1.3 Missing Data

No missing data will be imputed.

## 1.4 Statistical Methodology

### 1.4.1 Data Summary

Descriptive statistics were computed for demographics parameters and study measures. For continuous data, the N, mean, median, standard deviation, interquartile range, minimum and maximum were computed. For categorical data, the frequency was computed. Correlation was calculated using Spearman's rank correlation coefficient.

Documentation of statistical analyses with Python v3.9.0 will be maintained.

#### **1.4.2 Sample Size Justification**

A sample size calculation was not performed for this observational study since the primary goals were to evaluate measures related to the usability of the Motionsense system.

#### **1.4.3 Interim Analyses**

No interim analysis is planned.

#### **1.4.4 Analysis Population**

The study population will include all non-censored subjects who have received the Motionsense and are available for objective analysis. The objective analyses will be based on the per protocol population.

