3.2 Patient Journey

The patients will be using the Motionsense system for up to 120 consecutive days during this study. During the study, the patients will be interacting with the **principal investigator (PI)**, **physiotherapist (PT)** and **research nurse (RN)** at the following time intervals:

- **Initial Checkpoint:** patient consent and enrolment
 - Introduction to the study and patient consenting by Principal Investigator
 - System introduction (involving IFU – see Appendix A) and installation by Research Nurse
 - Initial, pre-operative exercise prescription (by Surgeon)
 - Evaluation of comorbidities (Charlson Comorbidity Index – Patient Reported)
 - Evaluation of expectations (HSS Expectations)
- **Pre-operative at home use:** prehab and questionnaires
 - Patient reported outcomes collected through app: KOOS and PROMIS-10 questionnaires
 - Daily pain scores
 - Pre-operative home exercise program completed
 - Pre-operative gait assessment (incl. use of walking aids)
 - Baseline activity data for activities of daily living (steps, weight bearing time, knee active time, range of motion)
- **Day of Discharge:** 2 to 3 days after surgery
 - Home exercise program updated by Surgeon
 - LACE questionnaire (Research Nurse)
- **Post-operative at home use:** home exercise and questionnaires
 - Patient reported outcomes collected through app: KOOS and PROMIS-10 questionnaires (at 2weeks / 6weeks / 90 days post-operative)
 - Daily pain scores
 - Post-operative gait assessment (2 times per week)
 - Post-operative home exercise program completed
 - Monitoring of daily activities

- **Outpatient Physiotherapist Visit:** starting 7-14 days after surgery
 - Home exercise program updated by Physiotherapist
 - Review of ADL activity by Physiotherapist
 - Changes in home exercise program documented and motivated in PT journal
- **Remote Monitoring:** throughout
 - Home exercise compliance and ADL activity level reviewed by Research Nurse / Surgeon
 - Logging of surgical complications (ER-visits / re-admissions / ...)
- **Final Checkpoint:** phone interview by Research Nurse
 - System compliance – evaluate moment of drop-off
 - Usability questionnaire including Net Promoter Score

Beyond these checkpoints with the health care professionals involved in the study, the patient will use the system on a daily basis and will be asked to fill out a daily pain score through the mobile application. The patient's daily flow while at home will look as follows:

- Wake-up

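### The SAP sets safety as all adverse events but names no safety population, and its only stated study population leaves out device recipients who are censored or unavailable

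*SAP*

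**What the plan says.** - **Safety scope.** SAP 1.2.1 is one sentence: "Safety parameters include all adverse events". It names no population, denominator or form of summary.
- **Population.** SAP 1.4.4 states: "The study population will include all non-censored subjects who have received the Motionsense and are available for objective analysis". It continues: "The objective analyses will be based on the per protocol population". Neither the terms for censoring and availability nor the per protocol set is defined, and there is no safety set.
- **Missing data.** SAP 1.3: "No missing data will be imputed". A patient left out of the population is therefore not brought back by another route.
- **Size.** Protocol 3.7: "A total of 50 participants will be recruited for the study". Protocol 3.1 gives 50 as a maximum. SAP 1.4.2 reports no calculation: "A sample size calculation was not performed for this observational study since the primary goals were to evaluate measures related to the usability".
- **Collection of events.** Protocol 3.2 has surgical complications, including emergency visits and re-admissions, logged throughout by remote monitoring. Protocol 3.8 adds a question on complications and re-admissions at the final interview, and the table in Protocol 5.0 has the surgeon clinic log complications after discharge.
- **Stopping use and skin harm.** The final interview is to "evaluate moment of drop-off" (Protocol 3.2). Among the selection criteria, Protocol 3.7 excludes severe skin conditions that could lead to "irritation or harming the skin when applying the weekly patches".

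**The concern.** Of the three conditions for entering the SAP 1.4.4 population, only receipt of the device is fixed at the start. The other two depend on what happens afterwards. For a safety summary this matters, because a skin reaction, a wound problem or a re-admission is a plausible reason for leaving the study or for having no usable sensor data. A population that requires patients to remain uncensored and available can therefore select on the outcome it is meant to count.

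At stake is whether the report delivers the scope that SAP 1.2.1 sets. With at most 50 patients, losing a few from the summary can change it visibly. Because the exclusion terms are undefined, who counts for safety could also be settled after the events are known.

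The point concerns the adverse-event summary only, not the compliance analyses.

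**Working it through.** **1. Which population does safety fall to?** SAP 1.2.1 names none. SAP 1.4.4 has two sentences: the first sets the study population in general terms, and the second ties the objective analyses to a per protocol set. The second does not reach safety. Safety is left with the first sentence or with no stated population, and neither secures a summary of all adverse events.

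**2. Is there a plan figure to reproduce?** No. The plan gives no event rate, withdrawal rate or sample-size calculation. The only number available is N = 50 (Protocol 3.7). Everything below is illustration.

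**3. Formula.** Let E be the patients with an event among N device recipients, k the excluded patients who had an event, and m the excluded patients who did not.

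- Rate in all recipients: E / N
- Rate in the restricted population: (E − k) / (N − k − m)

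The restricted rate is lower when k/(k + m) exceeds E/N, that is, when events are more common among those excluded than overall. It is higher when the reverse holds.

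**4. Results with assumed counts, N = 50** (exact Clopper-Pearson 95% intervals in brackets):

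| E | k | m | All recipients | Restricted population |
|---|---|---|---|---|
| 3 | 1 | 0 | 3/50 = 6.0% (1.3–16.5) | 2/49 = 4.1% (0.5–14.0) |
| 3 | 3 | 0 | 3/50 = 6.0% (1.3–16.5) | 0/47 = 0% (0–7.5) |
| 5 | 1 | 0 | 5/50 = 10.0% (3.3–21.8) | 4/49 = 8.2% (2.3–19.6) |
| 5 | 3 | 0 | 5/50 = 10.0% (3.3–21.8) | 2/47 = 4.3% (0.5–14.5) |
| 5 | 5 | 0 | 5/50 = 10.0% (3.3–21.8) | 0/45 = 0% (0–7.9) |
| 5 | 3 | 5 | 5/50 = 10.0% (3.3–21.8) | 2/42 = 4.8% (0.6–16.2) |
| 5 | 0 | 5 | 5/50 = 10.0% (3.3–21.8) | 5/45 = 11.1% (3.7–24.1) |
| 10 | 5 | 0 | 10/50 = 20.0% (10.0–33.7) | 5/45 = 11.1% (3.7–24.1) |

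**5. Reading.** The direction follows the link between exclusion and harm. In the row with k = 3 and m = 5, 3/8 = 37.5% of those excluded had an event against 10.0% overall, so the rate falls even though most exclusions were event-free. With k = 0 it rises. SAP 1.4.1 promises frequencies for categorical data. If those are bare counts, the direction is no longer in doubt: the count drops from E to E − k and cannot rise.

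**The case against.** The strongest reply is that SAP 1.4.4 was never meant for safety. Its first sentence speaks of availability for objective analysis, which echoes the heading of SAP 1.1.1, where the study objectives are listed and safety is not among them. Safety has its own section, with no restriction. On that reading SAP 1.4.4 governs the objectives and every recipient counts for adverse events. This is a coherent reading and nothing in the SAP rules it out. But the first sentence is worded as the population of the study as a whole, and no other is offered for safety. If the sponsor holds this reading, the SAP still needs to say so.

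Other parts of the reply stand and limit the point:

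- **Stopping wear is not shown to be censoring.** A reader might infer that any patient who stops wearing the sensors leaves the safety summary. The documents do not support that. The drop-off item belongs to the final interview, so it concerns patients who are still in contact and who, under Protocol 3.8, are also asked about complications.
- **Skin harm is not described as an expected reason for withdrawal.** The wording in Protocol 3.7 is a selection criterion that keeps predisposed patients out. It shows the risk was recognised, and no more.
- **Collection is not the gap.** Complications are logged whatever the patient's wear. The gap is in who is analysed.
- **Stakes are modest.** This is a single-group descriptive study, and safety is not among its listed objectives. Wound complications and re-admissions also mainly reflect the surgery, so they say little about the device.
- **Reasons for stopping are not a named data item.** A full count of patients who stopped because of an event may not be obtainable from the planned records.

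**Conclusion.** The point holds in conditional form. The SAP sets a safety scope of all adverse events and then states one general population that, applied literally, can omit patients who withdrew or became unavailable. If safety is summarised in that population, and if exit is related to harm, the reported rate is too low. In the central illustration it is 4.3% instead of 10.0%. Across the assumed cases the restricted rate ranges from no visible events at all to a slight overstatement (11.1% instead of 10.0%) when only event-free patients are excluded.

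Three assumptions carry this: that SAP 1.4.4 governs safety, that leaving because of harm makes a patient censored or unavailable, and the counts themselves. The first is implied by the absence of any alternative, the second is possible but not stated, and the third cannot be taken from the documents. A reader might infer that the device will be reported as safer than it is. The documents do not support that as a prediction. They show only that the stated rule permits it. The ambiguity should be closed before analysis, because the remedy is concrete and nearly free.

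**What to change.** In SAP 1.4.4, add a safety population and confine the existing restriction to the objectives. Suggested text:

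> Safety population: every patient who had a MotionSense patch applied at least once, whether or not later censored, withdrawn or unavailable. The requirements of being non-censored and available apply to the objective analyses only.

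Define censored, available and per protocol in the same section, and report the number of patients excluded from each set, with reasons.

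In SAP 1.2.1, add:

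> Adverse events and logged complications are reported as number and percentage of patients in the safety population, including events before withdrawal. Surgical complications are shown separately from device-related events. Events leading to discontinuation are reported where the reason was recorded.

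**Cost.** A few sentences in the SAP and no change to visits or care. The summary draws on complication and clinic-contact records already called for in Protocol 3.2, 3.8 and 5.0. Skin reactions and reasons for stopping are not named there, so those entries may be incomplete unless collection is extended. The event rate may look less favourable. Patients who withdrew will have incomplete follow-up, so the length of follow-up and the number not followed to 90 days should be reported beside the rates.

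### SAP 1.4.4 assesses the primary compliance objective in an undefined per-protocol set, with no analysis of all device recipients, so patients may be selected on the outcome being measured

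*SAP*

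**What the plan says.** SAP 1.1.1, headed Objective Analysis, puts this first among the primary objectives: "Evaluate patient and practice compliance with the MotionSense wearable system". The items under it include days of use before and after surgery, filled-out questionnaires and the home exercise program.

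SAP 1.4.4 sets the analysis population in two sentences. The first describes a study population of "all non-censored subjects who have received the Motionsense and are available for objective analysis". The second adds: "The objective analyses will be based on the per protocol population". Neither document says what makes a patient per protocol, censored or unavailable. Neither sets a minimum wear time or a completion rule, and neither plans a second or sensitivity analysis in all recipients.

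Three other places bear on the point:

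- SAP 1.3: "No missing data will be imputed".
- SAP 1.4.1: "For continuous data, the N, mean, median, standard deviation, interquartile range, minimum and maximum were computed".
- Protocol 3.2, under the final phone interview: "System compliance – evaluate moment of drop-off".

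**The concern.** A per-protocol set ordinarily keeps patients who did what the protocol asked. Here, doing what was asked is the outcome. If patients who wear the device little, or give it up, leave the analysis set, the compliance estimate describes those who complied. The patients who stopped carry much of the information a usability study is after.

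Patient use is a primary result, and two analysts could apply 1.4.4 differently and report different compliance from the same patients, of whom there are at most 50. The study is descriptive, with no threshold or comparator. What is at stake is therefore a misleading usability estimate, not a wrong test decision.

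**Working it through.** **Reading the text**

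1. The heading of SAP 1.1.1 shows that the objective analyses of 1.4.4 are the analyses of the listed objectives, so they include OBJ1.1.
2. The first sentence of 1.4.4 comes close to an all-recipient set, but non-censored and available narrow it. No time-to-event analysis or censoring rule appears elsewhere to give *censored* a meaning.
3. The second sentence moves the analyses to per protocol. No rule follows.
4. The final interview asks when use dropped off, so the protocol foresees that some patients will stop. It gives no rate, and nothing says whether these patients are analysed.

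**Size**

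The documents give no compliance, drop-off or exclusion figure, so there is none to reproduce. Let p be the share of recipients left out, and let U_kept and U_excl be the mean share of days worn in kept and excluded patients. Then:

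- All-recipient mean = (1 − p) × U_kept + p × U_excl
- Overstatement = U_kept − all-recipient mean = p × (U_kept − U_excl)

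This is 0 when U_kept = U_excl and positive when low users are left out.

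*Illustration 1 (assumed inputs).* N = 50, D = 90 post-operative days, U_kept = 0.80, so the per-protocol mean is 0.80 × 90 = 72.0 days. Overstatement in days = 90 × p × (0.80 − U_excl).

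| Excluded | All-recipient mean, U_excl = 0.50 | Overstated by | All-recipient mean, U_excl = 0.20 | Overstated by |
|---|---|---|---|---|
| 10% (5 patients) | 69.3 | 2.7 | 66.6 | 5.4 |
| 20% (10) | 66.6 | 5.4 | 61.2 | 10.8 |
| 30% (15) | 63.9 | 8.1 | 55.8 | 16.2 |
| 40% (20) | 61.2 | 10.8 | 50.4 | 21.6 |

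With U_excl = 0.80, every overstatement is 0. D = 90 is a simplification: Protocol 3.2 puts discharge 2 to 3 days after surgery, which leaves 87 to 88 days. The largest entry would then be 87 × 0.4 × 0.6 = 20.9 to 88 × 0.4 × 0.6 = 21.1.

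*Illustration 2 (assumed inputs).* Suppose the rule were itself a wear threshold t, with wear share distributed as Beta(3,2), mean 0.6, or 54.0 of 90 days. The share kept is 1 − (4t³ − 3t⁴). The mean in those kept is [0.6 − (3t⁴ − 2.4t⁵)] divided by the share kept.

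- t = 0.5: kept 0.6875; mean 0.4875 / 0.6875 = 0.709, or 63.8 days (+9.8).
- t = 0.7: kept 0.3483; mean 0.2831 / 0.3483 = 0.813, or 73.1 days (+19.1).

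Under a wear threshold that excludes anyone, the overstatement is positive by construction.

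**What the no-imputation rule changes**

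In a plain count of days used, a day without use adds nothing. In a count of filled-out questionnaires, an unreturned one is not counted. SAP 1.3 alters neither. The rule matters once use is given as an average per day or a percentage, because the plan does not say whether a non-use day enters as zero or drops out. Such a figure also needs each patient's own dates, since follow-up is defined as "starting 2-4 weeks prior to surgery up to 90 days after surgery" and its length differs between patients.

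**The case against.** The best defence is that the second sentence of 1.4.4 only renames the set in the first. The stated criteria are receipt of the system, non-censoring and availability. No wear minimum exists anywhere, and asking about drop-off suggests that patients who stop remain in follow-up. On that reading nobody is excluded for low use and there is no bias.

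This is a possible reading, and it is why the direction can only be stated conditionally. It does not remove the problem. The two undefined filters could still drop patients who stop, and the text does not rule that out.

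It can also be said that N will be reported. That makes a shortfall partly visible, but shows neither how many received the system nor why patients were left out.

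A reader might go further in three ways that the documents do not support:

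- *The no-imputation rule itself inflates the counts.* It does not, as shown above.
- *The initial patch supply in Protocol 3.6 shows how large the bias is.* Refills are available from the clinic. Comparing a patient who never asks for one with full wear is also not a comparison of kept with excluded patients.
- *The four-week window in Protocol 3.7 is a further onboarding schedule, giving another day denominator.* It is an eligibility criterion and is compatible with the start time in 3.1.

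**Conclusion.** The concern holds in conditional form. The primary compliance objective is to be analysed in a set whose membership rule is not stated and may depend on compliance, with no all-recipient analysis beside it. If low users or patients who stop are left out, days of use, questionnaire completion and home-exercise compliance are overstated. If exclusions are unrelated to use, the bias is zero.

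A reader might infer that the reported figures will certainly be too high. The documents do not support that, because the exclusion rule is undefined. Nor can the size be derived from them: 2.7 to 21.6 days of 90 is an illustration resting on assumed exclusion shares and wear rates. This should be fixed before analysis. Confidence is moderate, because the authors may have meant all recipients.

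**What to change.** In SAP 1.4.4:

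- Make all enrolled patients who received the system the primary set for the patient-use items of OBJ1.1, including those who stop, withdraw or are lost.
- Keep the per-protocol set as supportive, with its exclusion rule stated. Define non-censored and available, or remove them.
- Report the numbers received, analysed and excluded, with reasons.

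In SAP 1.3, for any use measure given as an average per day or a percentage:

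- Count a non-use day within the patient's own expected-use period as zero. Take that period from the patient's onboarding, surgery, discharge and day-90 dates.
- Count a questionnaire that was due but not returned as not completed.

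The cost is a few sentences and one extra table. Protocol 3.8 already records hourly wearing time, exercise completion and questionnaires through the app. The downside is that compliance may look less favourable.
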